## **5.0 Pre-treatment evaluation**

(must be completed within 8 weeks prior to the completion of second step enrollment in CORe; In the event that a patient cannot be seen in person to consent and is consented remotely, physical exam and vitals are not required prior to enrollment. KPS/ECOG maybe conducted from the telephone calls. Baseline labs could be drawn at outside facility and IIEF-5 questionnaire can be completed at home and both can be submitted via secure email or fax.)

A. History and Physical, including KPS or ECOG. Include the following information at a minimum:

1. Age
2. Race and ethnicity
3. T-stage, N-stage, M-stage, Gleason score, initial PSA, PSA prior to radiation
4. Radiation therapy details:

- a. treatment dates
- b. modality: protons, photons, brachytherapy (include isotope used and dose), or any combination of these modalities
- c. for external beam (photon, proton, or combination):
  - 1. include whether or not pelvic lymph nodes were treated, and if so, report total and daily dose/fraction
  - 2. report total dose and dose per fraction for treatment to prostate +/- seminal vesicles
- 5. Most recent androgen deprivation therapy: report dates of treatment and drugs used
- 6. smoking history
- 7. alcohol history
- 8. current medications including non-prescription substances will be recorded in the medical chart.
- 9. Most recent treatment tried for ED
- 10. complete past medical history including history or presence of diabetes mellitus, hypertension, hyperlipidemias, endocrinopathies, cardiovascular diseases (e.g., coronary artery disease, CVA, TIA), hematologic diseases and psychiatric conditions will be recorded in the medical chart.
- 11. history of prior abdominal &/or pelvic surgery
- 12. current relationship status (i.e., married, widowed, divorced, presence of significant other)

B. Baseline assessment of erectile function using IIEF-5.

C. Laboratory studies: serum testosterone, CK, liver panel, BUN, Creatinine, GFR estimation, CBC, INR, PT, PTT

D. Baseline CTCAE V4.03 items grade 2 or higher: blurry vision, abdominal distension, abdominal pain, bloating, diarrhea, dyspepsia, flatulence, gastrointestinal pain, nausea, vomiting, malaise, pharyngitis, urinary tract infection, bruising, arthralgias, bone pain, generalized muscle weakness, myalgia, headache, rash (maculopapular), flushing

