**Table 1: Patient assessment schedule**

Test	Baseline *** (within 8 wks of enrollment)	6 wk* ± 2 wks	3 mo* ± 2 wks	6 mo* ± 2 wks	9 mo* ± 2 wks	12 mo* ± 2 wks	18 mo ± 4 wks*
H&P	X			X		X	X
BP, Pulse, Respiratory Rate	X	X	X	X	X	X	
KPS or ECOG	X			X		X	
IIEF-5****	X		X	X	X	X	
CTCAE V4.03**	X	X	X	X	X	X	
Hepatic panel	X	X	X	X	X	X	
CK 	X	X	X	X	X	X	
BUN, Creatinine, calculated GFR, CBC, PT, PTT, INR, Testosterone	X	X	X	X	X	X	

In addition to scheduled testing, obtain at any time patient notes muscular symptoms

\*follow up times start from the day patient begins taking all 3 drugs concurrently. Can be done over the phone or in person, in the event that follow up can only be done over the phone, physical exam, KPS or ECOG, and vitals do not have to be obtained. Labs could be drawn at outside facility and IIEF-5 questionnarire can be completed at home and both can be submitted via secure email or fax.

\*\*selected items with CTCAE grade 2 or higher: blurry vision, abdominal distension, abdominal pain, bloating, diarrhea, dyspepsia, flatulence, gastrointestinal pain, nausea, vomiting, malaise, pharyngitis, urinary tract infection, bruising, bleeding, arthralgias, bone pain, generalized muscle weakness, myalgia, headache, rash (maculopapular), flushing, chest pain, palpitations, dyspnea, cough, wheezing, lower extremity edema. This assessment can be done either over the phone or in person.

\*\*\*please refer to section 5.0 for pre-treatment evaluation

\*\*\*\*please refer to the appendix for the IIEF-5 questionnaire

D. **Modification of statin dosing**

1. discontinue if transamimases become  $\geq$  3 times ULN
2. discontinue if creatine kinase becomes  $\geq$  5 times ULN
3. If not on a statin prior to enrollment in the trial, discontinue if signs or suspicion of cardiovascular issues appear per the discretion of the treating physician.

For other side effects listed in section 8 above:

- a. if dose is  $\geq$ 20mg and if toxicity is Grade 2, decrease dosage by 50%. If toxicity resolves or decrease to Grade 1, maintain atorvastatin at this lower dose. If toxicities are  $\geq$ Grade 3, stop atorvastatin and the patient should be removed from the study.
- b. If dose=10mg, hold atorvastatin. If toxicity resolves or decrease to Grade 1, restart at 10 mg every other day. If toxicities are  $\geq$ Grade 3, stop atorvastatin and the patient should be removed from the study.

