## **10.0 Adverse Events**

An adverse event is the appearance or worsening of any undesirable sign, symptom, or medical condition occurring after the first protocol intervention, even if the event is not considered to be related to study treatment. Medical conditions/diseases present before starting study therapy are only considered adverse events if they worsen after starting study treatment. Abnormal laboratory values or test results constitute adverse events only if they induce clinical signs or symptoms, are considered clinically significant, or require therapy.

The investigator (or physician designee) is responsible for verifying and providing source documentation for all adverse events  $\geq$  grade 2 and assigning the attribution for all adverse events  $\geq$  grade 2 for subjects enrolled.

---

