### **ii. Adverse Events**

Patients' adverse events will be recorded by CTCAE v 4.03 at baseline and throughout this trial and at 30 days after stopping the active treatment portion of this trial (1 year on PAVE).

iii. Use of other ED treatment after PAVE.

ED treatment medications prescribed during or upon leaving this trial will be collected at 18 months

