**E. Analysis Plan**

Patients' baseline ED levels will be reported along with the proportion for patients who improve by at least 1 level according to the IIEF-5 for each time point measured. The proportion will be reported along with a 95% credible interval implementing a non-informative prior of beta(0.33, 0.67). Additionally, the proportion of patients who ever improve by at least 1 level will be reported overall. For secondary measures, the safety profile of the PAVE combination will be reported overall and for each planned subgroup based on prior statin treatment, with adverse events summarized by grade and time to onset to first grade 3 adverse event. Finally, the number of patients who drop out of the study to start an ED prescription medication will be reported. Exploratory analyses will be utilized to determine whether baseline patient features can predict response to PAVE or adverse events.

The Investigator is responsible for completing an efficacy/safety summary report, and submitting it to the IND Office Medical Affairs and Safety Group, for review and approval. This should be submitted every 10 evaluable patients, complete 8 weeks of study treatment until enrollment is complete

A copy of the summary should be placed in the Investigator's Regulatory Binder under "sponsor correspondence".

Important medical events as defined above, may also be considered serious adverse events. Any important medical event can and should be reported as an SAE if deemed appropriate by the Principal Investigator or the IND Sponsor, IND Office.

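### Section 5.0 D and Table 1 give different baseline CTCAE checklists (21 items against 28) and should be reconciled, along with two smaller gaps in the safety plan

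*Combined protocol and SAP*

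**What the plan says.** Section 5.0, item D, gives the pre-treatment checklist. It opens "Baseline CTCAE V4.03 items grade 2 or higher" and closes "urinary tract infection, bruising, arthralgias, bone pain, generalized muscle weakness, myalgia, headache, rash (maculopapular), flushing". In that closing run bruising is followed directly by arthralgias, so bleeding is not listed, and nothing follows flushing.

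Table 1 in section 8.0 has a CTCAE row marked at baseline, 6 weeks, and 3, 6, 9 and 12 months. The row's double-asterisk footnote gives its own item list, with bleeding placed after bruising and six further items at the end: "chest pain, palpitations, dyspnea, cough, wheezing, lower extremity edema". The baseline column carries a triple-asterisk footnote: "please refer to section 5.0 for pre-treatment evaluation".

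Section 11.0 B.ii asks for CTCAE recording at baseline and throughout, without an item list. Section 10.0 says that conditions present before therapy "are only considered adverse events if they worsen after starting study treatment".

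Two related statements belong to the same safety plan. Section 11.0 B.ii also requires adverse event recording "at 30 days after stopping the active treatment portion of this trial (1 year on PAVE". Section 11.0 E summarises "time to onset to first grade 3 adverse event", whereas section 11.0 D defines trial-limiting toxicity (TOX) as grade 3 or higher.

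**The concern.** The trial has one arm, and the Trial Summary names each patient's own baseline as the control. For the safety profile, a secondary objective, whether a symptom is new or worse depends on what was recorded before treatment. If the checklist used at baseline is shorter than the one used on study, the worsening rule in section 10.0 cannot be applied uniformly.

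The items in dispute matter to this plan. Section 8.0 B lists bleeding as a possible side effect of Vitamin E. Section 8.0 G.4 attaches dose modification and a cardiovascular evaluation to grade 2 cardiovascular toxicity. A long-standing grade 2 symptom with no baseline entry could be recorded as a new event.

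The other two gaps also concern whether the reported safety data match what the plan intends: one assessment is required but not scheduled, and one summary is worded so that the most severe first events fall outside it.

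**Working it through.** **1. Item count.** Inputs: the list in section 5.0 D and the list in the Table 1 double-asterisk footnote, compared item by item.

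- Section 5.0 D: 21 items.
- Table 1 footnote: 28 items.
- In Table 1 but not in 5.0 D: bleeding, chest pain, palpitations, dyspnea, cough, wheezing, lower extremity edema. 28 − 21 = 7.
- In 5.0 D but not in Table 1: none.

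Aligning 5.0 D to Table 1 takes the baseline list from 21 to 28 and the difference from 7 to 0.

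**2. Which list governs at baseline.** The row footnote and the X under baseline point to 28 items. The column footnote sends the reader to section 5.0, which has 21. Neither footnote says that it overrides the other, and 11.0 B.ii does not settle the matter.

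**3. What the difference does to one man.** Suppose he has grade 2 dyspnea before treatment and grade 2 dyspnea at 6 weeks. Under the 28-item list the baseline entry shows no worsening, so under section 10.0 it is not an adverse event. Under the 21-item list there is no baseline entry, and the classification rests on the medical history and the investigator's judgement.

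**4. Stopping rules.** The plan's own figures were reproduced first.

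- Toxicity: smallest x with P(p > 0.30 | Beta(1 + x, 1 + n − x)) > 0.95. At n = 10, 20, 30, 40 this gives 6, 10, 14, 17, as stated.
- Futility: largest x with P(p < 0.33 | Beta(0.33 + x, 0.67 + n − x)) > 0.975. This gives 0, 2, 5, 7, as stated.
- Probability of stopping early, by exact binomial convolution over the four looks with toxicity and response independent: 0.172 at true toxicity 0.30 and response 0.33 (stated 0.17). All 25 stated probabilities agree within rounding.

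None of these inputs involves the checklist, so the fix changes none of them. Misclassified events could reach the rule only by raising the apparent TOX rate. As an illustration with assumed rates that are not in the documents, a rise of 0.05 changes the probability of a toxicity stop as follows:

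| True TOX rate | Apparent rate | Probability of toxicity stop |
|---|---|---|
| 0.10 | 0.15 | 0.0002 → 0.0016 |
| 0.20 | 0.25 | 0.009 → 0.037 |
| 0.25 | 0.30 | 0.037 → 0.116 |

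A rise of 0.05 means 0.05 × 40 = 2 extra men by the last look, each with a pre-existing symptom recorded as grade 3 or higher, at least possibly related, and arising in the first 8 weeks. The effect is visible only when the true rate is already close to the 30% limit.

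**5. The 30-day assessment.** Table 1 has columns at baseline, 6 weeks, and 3, 6, 9, 12 and 18 months. For a man who stops at 12 months, the 12-month window closes 14 days later, which is 30 − 14 = 16 days before the assessment is due. The next column is 18 months (± 4 weeks) and has no CTCAE mark. No column therefore carries the assessment. The wording in 11.0 B.ii ties it to one year on treatment, which leaves men who stop early unclear.

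**6. Time to onset.** Read literally, a man whose first severe event is grade 4, with no earlier grade 3, has no event in the 11.0 E summary, although he counts as TOX under 11.0 D if the event is at least possibly related and falls in the first 8 weeks.

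**The case against.** The strongest reply is that Table 1 already requires all 28 items at baseline. Its CTCAE row is marked there and carries the longer list, and the column footnote may be no more than a pointer to the remote-consent, history and laboratory detail in section 5.0. This is a fair reading, and for that reason a reader should not infer that the seven items definitely have no baseline grade. The documents support a conflict. They do not establish that the assessment is absent. The conflict still needs removing, because a site working from section 5.0 would follow the short list.

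A second reply is that other provisions limit the harm. Section 5.0 requires a complete past medical history, including cardiovascular and hematologic disease. Investigators attribute every event of grade 2 or higher, and several exclusion criteria remove men at bleeding or cardiac risk. These points reduce the problem without closing it. The history records diseases, not symptom grades, and names no pulmonary disease. Remotely consented men need no physical examination or vitals. Attribution and the worsening rule both work better with the graded baseline that is in doubt. It is also fair that the cardiovascular rules in section 8.0 refer to cardiovascular issues and not to the checklist, so the link between them is an inference.

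On the smaller gaps, 11.0 B.ii does plan the 30-day assessment, section 10.0 separately captures serious events to 30 days after the last dose, and 11.0 E also summarises events by grade, so grades 4 and 5 would still be reported. These are wording and scheduling gaps, and the information is not wholly lost.

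**Conclusion.** The point holds as an internal conflict: 21 baseline items in section 5.0 D against 28 in Table 1, differing by bleeding and all six cardiopulmonary items. If a site follows 5.0 D, the rule on pre-existing conditions may lack a graded baseline for those seven. The likely consequence is less reliable attribution of grade 2 events and a less interpretable descriptive safety profile.

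Three stronger conclusions are not supported.

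- A reader might infer that the toxicity stopping rule is compromised. Its boundaries and operating characteristics reproduce and do not depend on the checklist. An effect would need several misattributed events of grade 3 or higher within 8 weeks.
- A reader might want a count of men affected. The documents give no prevalence for these symptoms, so no count can be defended.
- A reader might take the absence of CTCAE at 18 months as an error. Planned recording ends 30 days after treatment, and 11.0 B.iii uses 18 months to collect other ED treatment.

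The 30-day scheduling gap and the grade 3 wording hold as minor companion corrections. Both rest on a literal reading of the text.

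**What to change.** - **Section 5.0 D:** replace the 21-item list with the 28-item list of Table 1, so that every item graded on study is also graded at baseline to the same grade 2 threshold. Ideally, keep the list in one place and refer to it from the other.
- **Section 11.0 E:** define the time-to-onset event as the first adverse event of grade 3 or higher, in line with the TOX definition.
- **Table 1:** add a column for the 30-day post-treatment adverse event assessment already required by 11.0 B.ii, and state that it also applies to men who stop before one year. Table 1 already allows the CTCAE assessment by phone.

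The cost is seven more checklist items at an existing visit, one phone contact that the plan already implies, and a few words in 11.0 E. Sample size, stopping boundaries and operating characteristics are unchanged.

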## **6.0 Registration Procedures**

This protocol utilizes a two-step enrollment in the MD Anderson Cancer Center CORe database.

Patients should be entered into the first-step CORe enrollment when consents are completed.

Upon completion of all required materials for enrollment, second step enrollment will be completed to fully enroll the patient in CORe. No protocol-related therapies may be administered until the patient is fully enrolled in CORe.

## **7.0 Drug therapy**

A. The HMG-coA reductase inhibitor used in this study will be Atorvastatin for patients not already on a different statin

B. Dosage: 10-80 mg PO once daily

1. Those patients not currently on a statin will receive 10 mg/d Atorvastatin
2. For those currently on a statin, the statin and dose will be maintained at the current dose, unless a change is indicated for management of hyperlipidemia.

[figure not shown]
- a. If patients in this category are not taking at least a moderate intensity LDL lowering regimen, as defined in Appendix F, the prescribing physician

will be contacted for permission to modify the drug regimen, and if permission is granted, the regimen will be modified accordingly.

- C. Vitamin E: 1000 international units PO once daily
- D. Pentoxifylline: 400mg PO three times per day
- E. Patients or their third party payers will be expected to cover the cost of the drugs.
- F. Medication intake will be annotated in a pill diary as noted in the corresponding

#### Appendix

- G. Prescribing algorithm:

Vit E+PTX= Vitamin E 1000IU/d plus Pentoxifylline 400mg tid; LFTs=liver function tests (AST, ALT, total bilirubin)

## 8.0 Patient Assessments (see table 1)

A. **Atorvastatin:** most common side effects (generally mild) nasopharyngitis, arthralgia, pain in extremity, diarrhea and urinary tract infection

1. Liver function tests: check at 6 weeks (+/- 2 weeks), 3 months (+/- 2 weeks), while taking any statin.
2. Creatine kinase : check at 6 weeks (+/- 2 weeks), 3 months (+/- 2 weeks) and each subsequent visit while on any statin

B. **Vitamin E:** possible side effects: nausea, diarrhea, stomach cramps, fatigue, weakness, headache, blurred vision, rash, and bruising and bleeding

**Pentoxifylline:** most common side effects: dyspepsia, diarrhea, headache, nausea, vomiting, abdominal discomfort, bloating, flushing.

**Table 1: Patient assessment schedule**

Test	Baseline *** (within 8 wks of enrollment)	6 wk* ± 2 wks	3 mo* ± 2 wks	6 mo* ± 2 wks	9 mo* ± 2 wks	12 mo* ± 2 wks	18 mo ± 4 wks*
H&P	X			X		X	X
BP, Pulse, Respiratory Rate	X	X	X	X	X	X	
KPS or ECOG	X			X		X	
IIEF-5****	X		X	X	X	X	
CTCAE V4.03**	X	X	X	X	X	X	
Hepatic panel	X	X	X	X	X	X	
CK 	X	X	X	X	X	X	
BUN, Creatinine, calculated GFR, CBC, PT, PTT, INR, Testosterone	X	X	X	X	X	X	

In addition to scheduled testing, obtain at any time patient notes muscular symptoms

\*follow up times start from the day patient begins taking all 3 drugs concurrently. Can be done over the phone or in person, in the event that follow up can only be done over the phone, physical exam, KPS or ECOG, and vitals do not have to be obtained. Labs could be drawn at outside facility and IIEF-5 questionnarire can be completed at home and both can be submitted via secure email or fax.

\*\*selected items with CTCAE grade 2 or higher: blurry vision, abdominal distension, abdominal pain, bloating, diarrhea, dyspepsia, flatulence, gastrointestinal pain, nausea, vomiting, malaise, pharyngitis, urinary tract infection, bruising, bleeding, arthralgias, bone pain, generalized muscle weakness, myalgia, headache, rash (maculopapular), flushing, chest pain, palpitations, dyspnea, cough, wheezing, lower extremity edema. This assessment can be done either over the phone or in person.

\*\*\*please refer to section 5.0 for pre-treatment evaluation

\*\*\*\*please refer to the appendix for the IIEF-5 questionnaire

D. **Modification of statin dosing**

1. discontinue if transamimases become  $\geq$  3 times ULN
2. discontinue if creatine kinase becomes  $\geq$  5 times ULN
3. If not on a statin prior to enrollment in the trial, discontinue if signs or suspicion of cardiovascular issues appear per the discretion of the treating physician.

For other side effects listed in section 8 above:

- a. if dose is  $\geq$ 20mg and if toxicity is Grade 2, decrease dosage by 50%. If toxicity resolves or decrease to Grade 1, maintain atorvastatin at this lower dose. If toxicities are  $\geq$ Grade 3, stop atorvastatin and the patient should be removed from the study.
- b. If dose=10mg, hold atorvastatin. If toxicity resolves or decrease to Grade 1, restart at 10 mg every other day. If toxicities are  $\geq$ Grade 3, stop atorvastatin and the patient should be removed from the study.

**E. Modification of Vitamin E dosing:**

1. If toxicity is Grade 2, decrease dosage by 50%. If toxicity resolves or decrease to Grade 1, maintain Vitamin E at this lower dose. If toxicities are  $\geq$ Grade 3, stop Vitamin E and the patient should be removed from the study.
2. Discontinue if signs or suspicion of cardiovascular issues appear.

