**G. Modification of drug dosing where side effect can't be attributed to one specific drug:**

1. Since the 3 study drugs have overlapping toxicities, circumstances may arise in which it is not clear which drug is responsible for the toxicity.
2. If the toxicities are  $\geq$ Grade 3, stop all 3 drugs and the patient should be removed from the study.
3. If toxicity is Grade 2, first reduce the dose of atorvastatin as per guidelines above. If after 1 week the toxicity has not decreased to Grade 1 or resolved, reduce the dose of Pentoxifylline as per guidelines above. If after an additional week the toxicity has not decreased to Grade 1 or resolved, reduce the dose of Vitamin E as per guidelines above. If after another week the toxicity has not resolved or decreased to Grade 1, all 3 drugs should be stopped and the patient should be removed from the study.

4. Cardiovascular issues: for toxicity of Grade 3 or higher, all 3 drugs will be discontinued, and the patient directed to the nearest emergency department for urgent evaluation. For toxicity of Grade 2, guidelines delineated in sections 8.G.1-3 above will be followed for drug dosing modifications, while concurrently obtaining a cardiovascular evaluation from the patient's cardiologist (if he has one), or his personal primary care physician. At the patient's preference, cardiology evaluation may be obtained at MD Anderson. Continuation on study medications will be contingent on cardiology approval.

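### For a Grade 2 cardiovascular event not attributable to one drug, 8.E.2 and 8.F.2 stop vitamin E and pentoxifylline while 8.G.4 steps doses down subject to cardiology approval, with no stated precedence

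*Combined protocol and SAP*

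**What the plan says.** All the relevant text is in Section 8.0 of the combined protocol and SAP.

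- **8.E.2 (vitamin E) and 8.F.2 (pentoxifylline)** are worded identically: "Discontinue if signs or suspicion of cardiovascular issues appear".
- **8.G** is headed "Modification of drug dosing where side effect can't be attributed to one specific drug". Its item 4 deals with cardiovascular events at two levels. At the upper level: "Cardiovascular issues: for toxicity of Grade 3 or higher, all 3 drugs will be discontinued". At the lower level: "For toxicity of Grade 2, guidelines delineated in sections 8.G.1-3 above will be followed for drug dosing modifications". A cardiovascular evaluation is obtained at the same time, and the patient may stay on study drugs only if cardiology approves.
- **8.G.3**, to which 8.G.4 points, sets the order of the steps. It opens: "If toxicity is Grade 2, first reduce the dose of atorvastatin as per guidelines above". It goes on: "If after 1 week the toxicity has not decreased to Grade 1 or resolved, reduce the dose of Pentoxifylline as per guidelines above". Vitamin E is reduced after one further week, and all three drugs stop after another week if there is still no improvement.
- **8.D.3 (statin)** is narrower: "If not on a statin prior to enrollment in the trial, discontinue if signs or suspicion of cardiovascular issues appear per the discretion". The discretion is the treating physician's.

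**The concern.** Stopping rules for a possible cardiovascular problem should give the same answer whichever paragraph the treating team opens first. Here they do not for one kind of event: Grade 2, cardiovascular, and not traceable to a single drug. A team working from 8.E.2 and 8.F.2 stops two of the three drugs. A team working from 8.G.4 leaves both unchanged at first and adjusts atorvastatin. Each team has followed the protocol.

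The situation is foreseeable. The footnote to Table 1 asks for Grade 2 or higher chest pain, palpitations, dyspnea and leg edema to be recorded at the visits from 6 weeks to 12 months, by phone if need be. Section 9.0 speaks of a research nurse at each study site, so different staff may rely on different paragraphs. What is at stake is mainly the consistent protection of patients. Secondarily, men with the same event could have different drug exposure in the safety and response summaries.

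**Working it through.** The plan gives no figure to reproduce. The check sets the rules side by side and takes one patient through each. He has a Grade 2 cardiovascular event, and the responsible drug is unclear.

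**Step 1: does the event trigger 8.E.2 and 8.F.2?** On their wording, yes. The trigger is a sign or suspicion of a cardiovascular problem. It names no grade and does not ask which drug is responsible.

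**Step 2: does it trigger 8.G.4?** Yes. It is unattributed, so it falls under the heading of 8.G, and it is Grade 2, so 8.G.4 sends it to 8.G.1-3.

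**Step 3: compare the instructions over time.** Week 0 is the day the event appears. The later times add the intervals in 8.G.3: 1; 1 + 1 = 2; 1 + 1 + 1 = 3 weeks. Each later 8.G row applies only if the toxicity has not fallen to Grade 1 or resolved.

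| Time | 8.E.2 and 8.F.2 | 8.G.4 via 8.G.3 |
|---|---|---|
| Week 0 | Vitamin E and pentoxifylline discontinued | Atorvastatin step only; the other two unchanged |
| Week 1 | Already stopped | Pentoxifylline reduced; vitamin E unchanged |
| Week 2 | Already stopped | Vitamin E reduced |
| Week 3 | Already stopped | All three drugs stopped |

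The columns differ from the first day, so no course of action satisfies both.

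**Step 4: how long can the difference last?** 8.G.4 has three possible outcomes.

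- Cardiology does not approve: the drugs stop on that decision, possibly before week 3. No deadline for the decision is given.
- The toxicity persists through every step: the drugs stop at about week 3.
- The toxicity falls to Grade 1 and cardiology approves: 8.G.3 calls for no further step. If this happens within the first week, vitamin E and pentoxifylline are never reduced and may run on for the rest of the year on PAVE (Section 11.B.ii).

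**Step 5: other grades.** At Grade 3 or higher, 8.G.4 stops all three drugs, so it agrees with 8.E.2 and 8.F.2. For Grade 1, or for a suspicion not yet graded, 8.G.4 gives no instruction, so there is nothing for 8.E.2 and 8.F.2 to contradict.

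**Step 6: monitoring rules.** Section 11.D defines TOX as Grade 3 or higher, at least possibly related, in the first 8 weeks. A Grade 2 event is not counted, so the toxicity boundaries (6, 10, 14 and 17 at 10, 20, 30 and 40 patients) do not depend on which paragraph is followed.

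**The case against.** The strongest defence is structural. Sections 8.D to 8.F are organized by drug, and 8.G is expressly for events with no clear culprit. A reader can take 8.E and 8.F to apply when that drug is thought responsible, and 8.G otherwise. There is a good parallel. 8.E.1 and 8.F.1 also carry no attribution wording and call for a reduction at Grade 2, while 8.G.3 delays those same reductions. Nobody would call that a contradiction for every Grade 2 toxicity, so item 2 of each section might be read with the same implied limit.

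This is plausible and it narrows the point to unattributed Grade 2 events. It does not remove it. Item 1 speaks of a toxicity, which in a drug-specific section is naturally that drug's toxicity. Item 2 is triggered by suspicion of a cardiovascular problem, whichever drug is responsible. The implied limit is nowhere written, and 8.G.3 itself sends the reader back to the earlier guidelines for the dose steps.

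A second defence is the approval condition, which means that 8.G.4 does not simply keep the patient on treatment. That is correct. But the evaluation runs alongside the dose steps, so the drugs continue in the meantime, and approval to continue presupposes that they have not already been stopped.

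The documents do not support four stronger readings that a reader might infer:

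- *That 8.G.4 grades every cardiovascular event.* It covers only Grade 2 and Grade 3 or higher, within the scope of 8.G.
- *That the difference is capped at 3 weeks.* Three weeks is the stopping time only if the toxicity persists through every step.
- *That 8.D.3 is a third conflicting order.* It is discretionary and limited to men not already on a statin, so it can coexist with 8.G.4 and any clash is weaker.
- *That trial results are shown to be affected.* TOX is unaffected, 8.E.2 and 8.F.2 do not say that the patient leaves the study, and no expected frequency of such events is given.

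**Conclusion.** The point holds for vitamin E and pentoxifylline, in a Grade 2 cardiovascular event that cannot be attributed to one drug. There the two sets of instructions differ from the first day and neither is given precedence. In time, the difference runs from a short interval, if approval is refused early, through about 3 weeks, if the toxicity persists, to the remainder of the treatment year, if it settles and cardiology approves. How many patients would be affected cannot be estimated from the documents.

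The consequence is uneven handling of a safety event and, possibly, uneven exposure among otherwise similar patients. A shift in the primary result or in the stopping rules has not been shown.

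Two assumptions matter. The first is that 8.E.2 and 8.F.2 mean what they say, without an unwritten attribution limit. The second is that the prescribing algorithm in Section 7.0 G, whose figure is not reproduced in the available text, does not settle the order of precedence. Its legend mentions only the vitamin E and pentoxifylline regimen and liver function tests.

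**What to change.** Reconcile 8.E.2, 8.F.2 and 8.G.4 so that, for each drug, each grade and each attribution status (attributed to that drug, or unclear), exactly one instruction governs. If 8.E and 8.F are meant only for events attributed to that drug, say so there and refer to 8.G.4 for the rest. If 8.E.2 and 8.F.2 are meant to apply regardless of attribution, amend 8.G.4 to match. Cross-reference the discretionary statin rule in 8.D.3 so that all three drugs are covered consistently.

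Which rule is right is a clinical decision for the sponsor and its clinicians, and no view is offered here. The cost is a change of wording in Section 8.0, with no added visits, assessments or patients.
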